In this amendment, we will change the enrollment and analysis plans of our randomized study (called part A). This will involve conducting the analysis and reporting of comparative data between intervention and control arms, with the same study endpoints as the initial proposal. The main reason for ending enrollment at this time is the long delay we are likely to face before a co-located intervention can be offered in a physical syringe service program space. Instead, we will adapt our intervention to be telemedicine-based for continued enrollment into a nonrandomized treatment group (Part B). After the end of follow-up for part B, we will describe outcomes and compare to the previously randomized control population, to test if telemedicine-based engagement is feasible, safe, and noninferior to the co-located intervention.

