### 4. **Section 3:** Study Design

**Change:** For participants entering in Part B, randomization will not occur. All participants will be assigned to the intervention arm, which we will call the telemedicine arm in this document.

**Rationale:** The part B telemedicine arm will not be randomized, and instead will be compared to previously randomized arms. This is in order to maximize sample size exposed to the intervention with the available remaining budget and grant period.

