## 9. **Section 8:** Statistical and Analytic Considerations

**Change:** Adding the Part B analysis for comparing the telemedicine arm to the previously enrolled study arms.

**Rationale for change:** We will compare the proportion of patients who achieve SVR12 in each Part B telemedicine to (1)Part A intervention (2) Part A control, using Chi-square or Fishers' exact testing, using an intention-to-treat approach in which participants are analyzed in the group to which they are randomized. Participants with negative confirmatory HCV RNA PCR tests on study entry will not be included in the analysis, consistent with our existing approach.

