#### 1.7 Secondary Outcomes

[figure not shown]
1. The proportion of participants who initiate treatment for HCV in the intervention arm compared to the usual care arm by study week 48.
2. The proportion of participants who complete the prescribed course of treatment for HCV in the intervention arm compared to the usual care arm by study week 48.3. The proportion of participants after initiating HCV treatment did not complete it compared to the usual care arm by study week 48.
4. The proportion of participants in both arms who achieve SVR 12, or are RNA negative at baseline, that have HCV reinfection (defined in section 5.5) by study week 48.
5. To characterize the HCV genotype and presence of resistance associated substitutions (RAS) in those treated patients with HCV reinfection or relapse.
6. To examine impact of engagement in HCV treatment on substance use behaviors and injection risk.
7. Qualitative assessment using semi-structured interviews to evaluate the acceptability of the intervention versus usual care, the barriers to initiate and complete treatment, and factors influencing successful treatment outcomes
8. To assess the feasibility, safety, and effectiveness of a tele-medicine based rapid start intervention for hepatitis C treatment in young people who inject drugs.

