### 3.0 Study Design

This is a single-center, open-label, randomized controlled trial, in which 72 HCV antibody positive participants between ages 18-29 will be recruited in two parts. During Part A, participants will be randomized to either the rapid treatment intervention arm, or the usual care control arm. During Part B, participants will be enrolled to the telemedicine arm. Recruited individuals must have used injection drugs in the past 30 days, have no medical contraindication to sofosbuvir and velpatasvir treatment, be HIV uninfected, and be HCV treatment naïve. During part B, they must have access to technology that allows telemedicine interventions (eg telephone, smartphone, or internet connection).

The goal of the study is to provide same-day, easily accessed medical evaluation and treatment to the intervention arm. During part A, participants randomized to the intervention will receive medical evaluation, laboratory assessment including confirmatory HCV RNA testing, baseline questionnaire/interview, and distribution of a 7-day medication “starter pack” on the day of enrollment. Participants who are HCV RNA negative will be notified by phone call, be asked to return their medications but continue to be followed for research visits every 12 weeks, similar to the control-arm. During part B, participants will have the option of an in-person evaluation at the syringe service program or a telemedicine visit on the day of enrollment or the following day. They will receive community based laboratory testing at a location that is convenient to them, and participate in study interview.

During part A, HCV RNA positive participants in the intervention arm will be asked to start medications, and return to pick up an additional 21-day supply. They will receive weekly text messages during treatment to record adherence. They will receive one follow-up medical visit at 4 weeks with laboratory evaluation, with distribution of the remainder of medications, and another visit at the end of treatment. One of these two visits (the participants’ choice) will include counseling for prevention of reinfection. They will then have HCV RNA PCR testing at end of treatment and 12 weeks post treatment, and at 48 weeks to assess for reinfection. Each study visit will include a brief questionnaire and qualitative interview.

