Participants in the control arm will be provided facilitated referral to community HCV providers by an on-site care coordinator already facilitating care at the community site. HCV RNA negative participants will be called to inform them of these results, and then discontinued from the study. HCV RNA positive participants will be asked during the semi-structured interviews as at 12, 24, 36 and 48 week if they engaged in HCV treatment to assess whether their HCV referral has been filled, and to record their current HCV treatment status. They will also receive repeat HCV RNA testing at week 12, 24, and 48. Participants that have started treatment will be asked to sign consent for release of medical records pertaining to HCV-related laboratory testing to determine achievement of treatment response.

During part B, HCV RNA positive participants will have a 28-day supply of medications delivered, or available for pickup, as they prefer. The schedule of visits will be similar except that laboratory testing at week 4 will be optional, and all visits will be offered through telemedicine.

The three arms will be compared for the main outcome of SVR12 using a modified intention to treat analysis in which participants will be analyzed in the group they are randomized except for those who are (a) discontinued due to HCV RNA negative status or (b) found to have previously undiagnosed HIV at enrollment. Secondary outcomes will be compared using the same modified intention to treat design.

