### 8 Statistical and analytic considerations

#### 8.1 Sample size

Our own data (and others) suggests a SVR12 rate of 85% in active PWID (30), and existing literature suggests the control arm will have a very low uptake of HCV treatment (12% initiate treatment). (16) Using these estimates and an alpha =0.05, we have 100% power to detect a difference. However given the available referral and linkage programs, the control arm may have better HCV uptake and SVR 12 rates than predicted by literature. Assuming 41% (11/27) of participants in the control arm achieve SVR12, we will have 80% power to detect an SVR of 78% in the intervention arm.

In addition to have an adequate sample size to compare the primary end point of SVR12 rates with the control arm, a sample size of 27 HCV infected participants in Rapid Treatment arm allows for 90% power to show with reasonable certainty that the underlying true SVR12 rate is greater than 60% in the Rapid Treatment arm, assuming that this true rate is actually 85%.

The table below also shows two-sided exact Blyth-Still-Casella (BSC) 90% CIs for potential observed SVR proportions for 27 enrolled participants. With a HCV infected sample size of 27 participants, the CI for the true SVR12 rate will be entirely above 60% if 21 or more of the 27 participants achieve SVR12.

Patients enrolled and found not to have detectable HCV RNA will be replaced. Assuming 75% of HCV antibody positive individuals will be infected with HCV (positive HCV RNA), we anticipate have to enroll roughly 36 participants in each arm to acquire 27 with confirmed viremia.

Observed SVR12 Rate	90% CI for True SVR12 Rate
85% (23/27)	(71%, 93%)
81% (22/27)	(65%, 90%)
78% (21/27)	(62%, 90%)
74% (20/27)	(58%, 85%)
70% (19/27)	(54%, 84%)
67% (18/27)	(50%, 80%)

As of this amendment, data from part A will be analyzed based on enrollment through March 1 2020, so the power to detect a difference will be reduced from the above calculation. This is due to the break in enrollment that was necessary during the COVID-19 pandemic.

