## 8.3 Data Analysis

### 8.3.1 Analysis of clinical outcomes data

For the primary analysis, after the completion of part A, we will compare the proportion of patients who achieve SVR12 in each arm using Chi-square or Fishers’ exact testing, using an intention-to-treat approach in which participants are analyzed in the group to which they are randomized. Participants with negative confirmatory HCV RNA PCR tests on study entry will not be included in the analysis.

For secondary analyses, we will:

- Compare the proportion of patients who achieve end-of-treatment response using Chi-square or Fishers’ exact testing
- Compare the proportion of patients who complete treatment, using Chi-square or Fishers’ exact testing
- Compare the proportion of patients who have HCV reinfection, using Chi-square or Fishers’ exact testing
- Describe adherence for participants in the Intervention arm only
- Describe demographic, clinical and behavioral factors for participants who have HCV reinfection or incident HCV infection

We will also perform the same analyses using an “as-treated” approach, in which participants in the intervention arm will not be included if they failed to initiate HCV treatment, or discontinued treatment for reasons clearly unrelated to the treatment intervention (e.g. relocation, incarceration).

After the completion of part B, we will compare the proportion of patients who achieve SVR12 in each Part B telemedicine to (1)Part A intervention (2) Part A control, using Chi-square or Fishers’ exact testing, using an intention-to-treat approach in which participants are analyzed in the group to which they are randomized. Participants with negative confirmatory HCV RNA PCR tests on study entry will not be included in the analysis.

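### The amendment says Part B will test whether telemedicine is noninferior to the co-located intervention, but the only planned analysis is an equality test with no margin and no confidence interval for the difference

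*Combined protocol and SAP*

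**What the plan says.** Section 0.1 sets out what will be done with Part B once follow-up ends: "compare to the previously randomized control population, to test if telemedicine-based engagement is feasible, safe, and noninferior to the co-located intervention". The sentence names the randomised control population as comparator, but the noninferiority claim concerns the co-located intervention.

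The objective in section 1.7, item 8, does not mention noninferiority: "To assess the feasibility, safety, and effectiveness of a tele-medicine based rapid start intervention".

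The analysis is in section 8.3.1: "we will compare the proportion of patients who achieve SVR12 in each Part B telemedicine to (1)Part A intervention (2) Part A control", by chi-square or Fisher's exact test. Section 0.2, item 9, introduces the same analysis ("Adding the Part B analysis for comparing the telemedicine arm to the previously enrolled study arms") with the same tests. Section 3.0 adds that "The three arms will be compared for the main outcome of SVR12 using a modified intention to treat analysis".

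None of these places gives a margin, a one-sided hypothesis, a confidence interval for the difference between arms, or a separate Part B sample size. The only intervals, in section 8.1, are single-arm 90% intervals for 27 participants.

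**The concern.** A chi-square or Fisher test takes equal SVR12 proportions as its null hypothesis. A noninferiority test takes as its null that telemedicine is worse by at least a stated margin. Failing to reject equality says nothing about that second null, and least of all in small samples. The planned test would imply noninferiority only if telemedicine came out significantly better, because the interval for the difference would then lie above zero and so above any negative limit.

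If the two delivery models perform alike, the expected result is p > 0.05. Under the aim in 0.1, that could be read as success while a large deficit for telemedicine remained plausible. An interval could be computed afterwards from the counts, but a margin chosen after seeing the data carries little weight.

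The comparison of telemedicine with Part A control is not affected.

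**Working it through.** **The plan's own figure.** Section 8.1 gives 80% power with 27 per arm for 41% v 78%. With the usual two-sided 0.05 formula without continuity correction, the mean rate is (0.41 + 0.78)/2 = 0.595 and

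n = [1.96·√(2·0.595·0.405) + 0.8416·√(0.41·0.59 + 0.78·0.22)]² / 0.37² = (1.361 + 0.541)² / 0.1369 = 26.4, so 27 per arm.

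Power at 27 is 80.9% by the formula, and by exact enumeration 80.2% (chi-square) or 72.1% (Fisher). The Part A figure reproduces. It is a superiority calculation, and there is no counterpart for Part B.

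**Arm sizes (assumed).** Section 3.0 describes a study "in which 72 HCV antibody positive participants between ages 18-29 will be recruited in two parts". Section 8.1 adds: "Assuming 75% of HCV antibody positive individuals will be infected with HCV". So 72 × 0.75 = 54 viremic participants. Part A is 1:1 (section 8.2), so if its intervention arm has k, its control arm also has k and telemedicine has 54 − 2k. I took k = 12 to 21, that is, telemedicine v Part A intervention from 30 v 12 to 12 v 21. The original target of 27 v 27 is an optimistic case, since section 8.1 says Part A stopped short.

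**Rates (assumed).** 78% and 85% are the two intervention-arm SVR12 rates in section 8.1. The 20-point deficit (58%) and the margins are illustrative.

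**Method.** Exact enumeration of both binomials. P(non-significant) is the sum of Bin(a; n₁, p₁)·Bin(b; n₂, p₂) over outcomes with two-sided p > 0.05. Noninferiority power is the same sum over outcomes whose Newcombe 95% lower limit for telemedicine minus co-located exceeds −margin.

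| Quantity | k = 12 to 21 | 27 v 27 |
|---|---|---|
| True 58% v 78%: non-significant, chi-square | 0.744–0.778 | 0.637 |
| True 58% v 78%: non-significant, Fisher | 0.785–0.843 | 0.742 |
| Both 78%: significantly better for telemedicine, chi-square | 0.020–0.039 | 0.028 |
| Both 78%: significantly better for telemedicine, Fisher | 0.010–0.023 | 0.010 |
| Both 78%: noninferiority power, 10-point margin | 0.071–0.143 | 0.146 |
| Both 78%: noninferiority power, 15-point margin | 0.152–0.256 | 0.279 |
| Both 78%: noninferiority power, 20-point margin | 0.262–0.408 | 0.451 |
| Both 85%: noninferiority power, 20-point margin | 0.279–0.493 | 0.539 |

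**Other rates.** With 85% v 65%, the test is non-significant in 58% (chi-square) or 72% (Fisher) of trials at 27 per group, and in 75% or 87% at 15 per group.

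**Worked example, 18 v 18.** Suppose 10/18 (telemedicine) v 14/18, a difference of −0.222.
- Chi-square: pooled rate 24/36 = 0.667, SE = √(0.667·0.333·2/18) = 0.157, z = 1.41, p = 0.157. Fisher p = 0.289.
- The Wilson limits are 0.337 to 0.754 and 0.548 to 0.910.
- Newcombe lower limit: −0.222 − √[(0.556 − 0.337)² + (0.910 − 0.778)²] = −0.478.
- Newcombe upper limit: −0.222 + √[(0.754 − 0.556)² + (0.778 − 0.548)²] = +0.082.

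The p-value shows no difference, yet a 48-point deficit is inside the interval. Identical results (14/18 v 14/18) still give −0.265 to +0.265.

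**Size needed with a margin.** With 85% in both groups, one-sided 0.025 and 80% power, n = (1.96 + 0.8416)²·2·0.85·0.15 / margin² = 2.001 / margin². This gives 201 per group for 10 points, 89 for 15, 51 for 20 and 23 for 30.

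**The case against.** The strongest reply is that noninferiority appears only in section 0.1, an introductory rationale. The operative objective (1.7, item 8) and the analysis (8.3.1) promise an assessment and a comparison, and they agree with each other. Part B is a secondary, non-randomised part of a pilot study. This stands as a reason to keep the point in proportion, and it makes the remedy easy. It does not remove the conflict: 0.1 belongs to the current amendment, describes future work, and sits beside the change that introduced the equality test.

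The sizes also rest on assumptions. The figure of 72 equals the original 36 per arm × 2, so it may be a carried-over Part A target and not a total for both parts. The range of k has no source in the document. That is fair, but the logical point does not depend on arm sizes, and the 27 v 27 case leads to the same conclusion.

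A noninferiority claim is not out of reach at every margin. With both rates at 85% and a 30-point margin, power is 82% at 30 v 12 and 85% at 27 v 27, though only 53% at 12 v 21. Whether so wide a margin would be acceptable is a separate judgement.

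Finally, a margin and an interval would not deal with confounding. Part B is non-randomised and later in time, and excludes people without telemedicine access (section 1.3.2). This also stands, so the comparison should be labelled non-randomised whichever remedy is chosen.

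**Conclusion.** The concern holds: on this point the plan is wrong as written. Section 0.1 states a noninferiority aim that the only planned comparison cannot meet unless telemedicine proves significantly better, and with equal true rates of 78% that happens in about 1–4% of trials. Over the assumed arm sizes, about three-quarters or more of trials with a true 20-point deficit would end with p > 0.05, and power at a 20-point margin stays below one half. These figures depend on assumed arm sizes, true rates and margins; the mismatch between aim and test does not. It should be fixed, but it concerns a secondary comparison and leaves the randomised Part A primary analysis intact.

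**What to change.** 1. In section 8.3.1, report telemedicine minus Part A intervention as an SVR12 risk difference with a 95% score-type confidence interval (for example Newcombe), and state that the comparison is non-randomised and non-concurrent.
2. Then choose one of two courses. The more realistic at this size is to delete the noninferiority wording from section 0.1 and call the comparison descriptive, in line with section 1.7, item 8. The alternative is to specify and justify a margin before Part B data are analysed, and to claim noninferiority only if the lower limit clears it, with the caveat on confounding attached.
3. As a small tidy-up, section 8.3.1 still analyses Part B participants by randomised group. Section 0.2, item 4, makes the intended set clear ("All participants will be assigned to the intervention arm, which we will call the telemedicine arm in this document"), so refer instead to the modified intention-to-treat set in section 3.0.

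The cost is a few sentences and one interval, with no new data. What is given up is a noninferiority claim that the likely sample could support only at a very wide margin.

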### 8.3.2 Analyses for qualitative data

A subset of patients will be selected for qualitative interview from each arm. Participants will be recruited using purposive sampling, aiming for diversity of demographic characteristics, HCV risk factors, and treatment outcomes. Qualitative interviews will be analyzed using content analysis, creating codes and synthesizing them into dominant themes.

